6.3 Missing Data

Missing data will be minimised by careful data management. Missing data will be described with reasons given where available; the number and percentage of individuals in the missing category will be presented by treatment arm. All data collected on data collection forms will be used, since only essential data items will be collected. No data will be considered spurious in the analysis since all data will be checked and cleaned before analysis.

Missing covariate data: If the amount of missing covariate data leads to exclusion of less than 5% of participants, and it is implausible that such exclusion is associated with outcomes or is not associated with observed outcomes, then missing data will be considered ignorable. Fully adjusted analyses will be based on all randomised using imputed covariate data using single conditional imputation. Sensitivity analyses will include adjusted analyses based on those with complete covariate profile.

If the amount of missing covariate data leads to more than 5% and auxiliary variables can be identified that are associated with missingness with predictive value for the missing data then multiple imputation will be employed, including observed outcomes, randomised treatment, auxiliary covariate data predictive of missingness and all variables which will be used in adjusted analyses. The imputation model will include all participants randomised in the group originally assigned.

Missing outcome data: The primary analysis method proposed is reasonably robust to missing at random (MAR) data [38] conditional on all outcome measurements on all other visits and other covariates included in the model (Table 1).

Drop-out indicators will be created and we will report the counts of participants dropping out by arm, as well as the follow-up visit they dropped out (Table 4a). For the purpose of our main analyses reporting outcomes up to 12 months, we consider a participant as having drop-out at a particular visit if all follow-up outcome assessments following that visit are all missing.

We will then examine any association of drop-out with important prognostic factors such as age, sex, nerve injury at presentation, BMI, diabetic status, smoking status, concomitant injuries which affect limb function, clinically significant SAEs relating to the interventions (Section 6.7), and baseline PROMIS scores as well as follow-up PROMIS scores observed before drop out. If significant associations are found with pre-drop out follow-up scores then we will fit an informative missingness model following Diggle & Kenward [39] (e.g. using xteregress and/or GLLAMM in Stata) where the longitudinal PROMIS scores will be modelled jointly with the

drop-out indicator. This analysis will be undertaken only if there is evidence of dependence of drop-out indicators on observed outcome data.

6.4 Sensitivity Analysis

Primary estimand: Average Treatment Effect (ATE) under a treatment policy strategy

Sensitivity analyses will be undertaken for the primary estimand [16] where all randomised patients will be analysed according to their treatment allocation and adjusting for treatment switching using **Propensity Score (Quantile) Regression adjustment.** Treatment switching post-randomisation due to individual patient and treatment characteristics prognostic of the outcome, can affect both the treatment effect and its precision, especially when the related covariate profile is highly unbalanced between the two groups. Inclusion of the propensity score of treatment received in the analysis model can adjust for such imbalances yielding more accurate effect estimates under the assumption that we have measured all confounding variables and that each participant has a nonzero probability to be treated with surgical fixation (positivity assumption) [18, 19, 40].

The initial step involves fitting the propensity score model. The propensity score model is a logistic regression model, modelling the probability of treatment received as a function of covariates that are prognostic for the outcome and individual participant characteristics associated with treatment receipt. The estimated Propensity Score (PS) derived from this model is an approximation of the true PS. Overfitting is not a problem in PS estimation as long as due diligence is applied to select covariates that are the most likely risk factors for the outcomes. Then this is used by each approach in different ways.

In the Regression adjustment approach, we include the quantiles of the propensity score in the analysis model as covariates and including treatment interactions with the PS-quantiles. This will correct imbalance and can reduce the standard error of the effect estimates [41, 42]. The balancing properties depend on the amount of overlap of the propensity score distribution in the two groups with associated bias-variance trade-offs whereby the more closely matched the comparison groups the less biased the treatment effect at the cost of increased variance.

The distribution of the PS for each randomised group will be examined graphically. IPTW balance will also be examined. The balance of the confounder after weighting the contributions of individuals (baseline and treatment characteristics used to model the PS) between those who assigned to surgical fixation and those assigned to functional bracing will be documented as standardised differences before and after weighting for each confounder used (e.g. using Stata's rebalance command). Although, there is no definitive value at which the treatment is considered unbalanced, a variance ratio less than 0.5 indicates that the data is not balanced and indicates the PS model may need to be revisited and/or trimming or removing data at the extreme of the distribution of the weights (e.g. the 5th and 95th percentiles) maybe needed.

The above estimator targets the average difference in PROMIS scores between the two groups (ATE). The resulting treatment effect represents the average difference in PROMIS scores we can expect if all participants in the target population were treated with non-operative treatment fixation instead of being treated with operative fixation [17].

Missing outcome data: The primary analysis method proposed is reasonably robust to missing at random (MAR) data [38]. Treatment effects will be compared to estimates resulting from the same model used in the primary (ITT) analyses after further adjusting for additional factors that are both prognostic of the outcome and associated with drop-out.

Informative drop out: Sensitivity analysis will also be undertaken on the primary analysis by imputing missing data under different missing not at random (MNAR) assumptions for the model targeting the ATE estimand and using the ITT population. This will be achieved using δ -based imputation following Cro et al. [43], where our primary is fitted and adding an offset δ -term with values set to the expected value of the missing data. This is done to assess the impact of unobserved participants having a worse or better response than those observed (e.g. implemented through the rctmiss Stata command) and is consistent with an ITT primary analysis. We will vary the values of the offset term using a range of different means (+/- 1 SD of PROMIS scores).

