| Treatment: Operative fixation vs non-operativ | e treatment |
|---|--|
| Estimand | Analysis |
| Target population | Analysis set |
| Children aged between 7 and 15 years who present at participating UK hospitals with a medial epicondyle fracture of the humerus. | All randomised participants. |
| Variable | Outcome measure |
| Physical Function measured on the child reported PROMIS Upper Extremity scale at 1-year post-randomisation. | Continuous outcome bounded scale (PROMIS Upper Extremity T-score) where higher scores indicate better function better function, at 12 months post-randomisation |
| Handling of intercurrent events | Handling of missing data |
| Switching Treatment arm: Participants who receive a different intervention to that which they were allocated will be analysed according to their randomised allocation Further surgery: Participants that require additional surgical intervention on their elbows are also considered part of the treatment All intercurrent events will be handled under a treatment-policy strategy ¹ . | Multilevel modelling of outcome scores over time, imputes implicitly intermittent missing data over the post- randomisation period of follow-up. The underlying assumption is missing at random (MAR) conditional on all other outcome scores and minimisation factors. This is the main approach to handling missing data. Sensitivity analysis : The MAR assumption can be strengthened by conditioning on additional baseline covariates predictive of the outcome and missingness. Missing data arising from participants discontinuing in the study prior to 12 months under a NMAR (Not Missing at random) informative missing data mechanism will be explored under two approaches: a) the extended Hausman-Wise-Diggle-Kenward selection model when drop out depends on outcome scores prior to drop out and where this is jointly modelled with the longitudinal outcome. b) using controlled multiple imputation: δ - based imputation (see section (Details in Section 6.3: Missing data) where the primary analysis model is augmented with an offset term with values set to the fixed values of the missing and repeated over |

a range (+/- 1 SD PROMIS score). This is done to assess the impact of drop-out on inferences

| Population-level summary measure | Analysis approach |
|---|---|

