3.2 Randomisation and Blinding

Patients will be randomised after consent. All hospital treatment areas have access to the internet so will access the randomisation service in real time i.e. there will be no delay in patient treatment.

Consenting participants will be allocated randomly (1:1) to either operative fixation or non-surgical treatment. Randomisation will be performed using a minimisation algorithm to ensure balanced allocation of participants across the two treatment groups, stratified by centre and dislocation status of the elbow at presentation in the emergency department (i.e. dislocated or not dislocated). The first 30 participants will be randomised using a simple randomisation schedule produced by the trial statistician, to seed the minimisation algorithm, and a non-deterministic probabilistic element will be introduced to prevent predictability of the treatment allocation.

Stratification by centre within the minimisation algorithm will help to ensure balanced treatment assignment within centre so that any unobserved factors (e.g. case-mix) contributing to between-centre variation in practices are balanced between treatment arms. The catchment area (the local population served by the hospital) will be similar for all hospitals; each hospital being a children's injury unit dealing with these fractures on a regular basis. All of the recruiting hospitals, and indeed all hospitals throughout the NHS, use these techniques as part of their normal practice i.e. staff will already be equally familiar with both forms of treatment. This cannot eliminate the clinician-specific effect of an individual at any one centre. However, since the procedures are commonplace across the NHS, many clinicians will be involved in the management of this group of patients; likely between 5 and 20 clinicians at each centre, including consultants and trainee surgeons. Therefore, we anticipate that each individual clinician will only treat a handful of those enrolled in the trial, reducing the risk of a clinician-specific effect upon the outcome in any one centre.

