3.3 Sample Size

Extremity Score for Children. Raw scores are translated into standardised T scores with a population mean of 50 and a Standard Deviation (SD) of 10. The 'Minimally Clinically Important Difference' (MCID) for the PROMIS Upper Extremity Score amongst children with milder forms of disability has been demonstrated to be three to

four [11], we seek to find a difference of four points. Assuming a SD of 10, a total of 266 patients (133 in each arm) is required to provide 90% power at the 5% level (two-sided) to detect a 4-point difference between the groups. Allowing for a conservative 20% loss to follow-up, we plan to recruit 334 patients in total for this trial (167 per arm).

The SD of 10 derived by PROMIS was based on a sample of children with a higher proportion of chronic illness than the general population [12], and it is anticipated that the variation in outcomes in the treatment of acute medial epicondyle fractures is likely to be less than in a chronic illness.

Independent verification of the sample size is available in

Z:\CSM_SCIENCE\Statistical Analysis\4. Sample Size**SCIENCE_SampleSize_Verification_04Apr2019.docx**, stored in the confidential statistical section of the TMF.

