6. ANALYSIS

The primary estimand of interest will be a treatment policy estimand (ITT population), using data from all randomised participants as randomised. This is chosen as the primary estimand to reflect the pragmatic nature of the study, and to identify the treatment effect regardless of any intercurrent events occurring. The elements of the primary estimand are summarised in Table 1.

The protocol also mandates a per-protocol analysis. The per-protocol analyses (section 4.2) will include all randomised participants who received their allocated treatment but excludes those randomised participants who were found ineligible post-randomisation, did not receive their allocated treatment.

Treatment switching as defined by NICE refers to the situation in a randomised controlled trial where patients switch from their randomly assigned treatment onto an alternative. Although it is widely recognised that ITT does not identify the true comparative effectiveness of the treatments under investigation there is disagreement on the acceptability of adjustment methods that can be used. Following NICE recommendations our ITT analyses is supplemented with further analyses in an attempt to adjust for switching [16] and described in section 6.4 sensitivity analyses.

The primary analysis and sensitivity analysis described in sections 6.2-6.4 focus on the primary estimand detailed in Table 1 which targets the average difference in PROMIS scores (ATE) between the two interventions in the combined groups randomised to receive each intervention. The resulting treatment effect represents the average difference in PROMIS scores we can expect if all participants in the target population were treated with non-operative treatment instead of being treated with operative fixation [17-19].

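### The propensity-quantile analysis in SAP 6.4 is labelled an adjustment for switching but estimates the same effect of allocation as the primary analysis, and both get an all-treated reading that Table 1 contradicts

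*SAP*

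**What the plan says.** Table 1 (SAP section 2) sets the strategy for the primary estimand: "All intercurrent events will be handled under a treatment-policy strategy". It says that children who switch are analysed in their randomised arm. It lists a propensity-score regression adjustment as a sensitivity analysis of that same ITT estimand.

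Section 6 gives the motive. It concedes that ITT does not identify how the treatments truly compare, and says that further analyses in section 6.4 will attempt to adjust for switching. It then interprets the primary and sensitivity results together as the average difference "we can expect if all participants in the target population were treated with non-operative treatment instead of being treated with operative fixation".

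Section 6.4 describes the analysis: "all randomised patients will be analysed according to their treatment allocation and adjusting for treatment switching using" propensity-score quantile regression. The score is a logistic model for treatment received, given prognostic covariates and participant characteristics. Its quantiles, and their interactions with treatment, are added to the analysis model. The section says that the estimator targets the average treatment effect, and reads it as the difference "we can expect if all participants in the target population were treated with non-operative treatment fixation instead of being treated with operative fixation".

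**The concern.** Three statements do not fit together: the contrast is by allocation, it is said to adjust for switching, and the result is read as the effect of everyone being treated one way instead of the other. A contrast between randomised arms keeps each child who switched in the allocated arm. Adding functions of baseline covariates can improve precision but does not move those children.

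The risk lies in interpretation. SAP section 4.2 points to the section 6.4 analyses when relevant deviations are frequent, with more than 5% of participants as its example. In that situation the section 6.4 result should sit close to the primary result whatever switching has done. A report could then present the agreement as robustness to switching, and present either figure as the effect of surgery as received.

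**Working it through.** **1. The plan's own figure.** SAP section 3.3 gives a difference of 4, SD 10, 90% power and 5% two-sided.

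- n per arm = 2 × 10² × (1.960 + 1.282)² / 4² = 131.3, so 132 by the normal formula.
- The noncentral t gives power 0.899 at 132 and 0.901 at 133, so 133 per arm, or 266.
- 133 / 0.8 = 166.25, so 167 per arm, or 334.

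The stated figures are reproduced.

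**2. What the allocation contrast estimates.** Let s_O and s_N be the proportions switching in the operative and non-operative arms, and let treatment received have a constant effect of 4. Then

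expected difference = 4 × [(1 − s_O) − s_N] = 4 × (1 − s_O − s_N).

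Power for a simple 12-month comparison at 133 per arm is Φ(difference / 1.226 − 1.960), where 1.226 = 10 × √(2/133). The documents give no switching rate, so the sums below are assumptions.

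| s_O + s_N | Difference | Power |
|---|---|---|
| 0% | 4.0 | 90% |
| 5% | 3.8 | 87% |
| 10% | 3.6 | 84% |
| 15% | 3.4 | 79% |
| 20% | 3.2 | 74% |
| 30% | 2.8 | 63% |

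With equal arms the overall proportion switching is half the sum. If every deviation at the SAP's 5% example were a switch, the sum would be about 10%, giving 3.6 points.

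**3. What the propensity quantiles add.** Let G be the quantile group of a score built from baseline covariates. Randomisation makes G independent of allocation. Averaging the between-arm difference within G over the distribution of G therefore returns the overall between-arm difference. The target is the ITT value, with or without the interactions.

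**4. Check by simulation.** Allocation was 1:1, the true effect of treatment received was 4, and total SD was about 10. Switching was driven by a measured prognostic covariate, so the SAP's assumption of no unmeasured confounding held. The score was entered as quintiles and averaged. Means at N = 20,000 (SD across replicates for ITT 0.10 to 0.13):

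| Switching, operative / non-operative | ITT | As randomised + quintiles (SAP 6.4) | Treatment received + quintiles | ITT ÷ difference in proportion receiving surgery |
|---|---|---|---|---|
| 5.5% / 5.7% | 3.63 | 3.60 | 3.95 | 4.09 |
| 11.2% / 10.9% | 3.16 | 3.17 | 3.92 | 4.06 |
| 20.3% / 9.3% | 2.76 | 2.76 | 3.81 | 3.92 |

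The formula in step 2 gives 3.55, 3.12 and 2.82 for these rows, in line with the ITT column. At N = 266 the section 6.4 analysis gave 3.73, 3.28 and 2.95 against ITT 3.58, 3.15 and 2.86. It was slightly higher but short of 4, against sampling SDs of about 1.2. Table 1 words the score differently, as the propensity of receiving the allocated treatment. That version gave 3.63, 3.16 and 2.75 at N = 20,000, again the ITT value.

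The last column returns about 4 because the effect was set constant. It shows what an estimator that uses treatment received can do under that assumption, and is not evidence about this trial.

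**5. The interpretation.** Under treatment policy the result is the effect of being allocated to one arm rather than the other, whatever is then received. The all-treated sentences describe full receipt of each treatment. The two are equal only if nobody switches (first row of the first table). Section 6 cannot hold both its concession about ITT and its all-treated sentence.

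**The case against.** The strongest reply is that section 6.4 is headed as a sensitivity analysis of the treatment-policy estimand, and Table 1 files it there. An analysis that stays at the ITT value is correct for that estimand. This stands: a reader might infer that the diluted difference makes the primary result wrong, and it does not.

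Four further inferences go beyond the documents.

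- **A diluted null would pass unchallenged.** A per-protocol analysis that excludes switchers is planned (SAP 4.2 and 6), the protocol's section 10.1 adds an as-treated analysis, and Table 8 reports receipt of allocation with reasons. These are open to selection bias, and SAP 4.2 defines no as-treated population, but they do not simply repeat the ITT result.
- **Agreement is guaranteed in every dataset.** It holds in expectation, for baseline covariates. Section 6.4 also mentions treatment characteristics among the variables used for the score. Those may arise after randomisation, and then the equality need not hold.
- **The interactions mean that a single reference-quantile effect will be reported.** The SAP does not say so. It says that the average is targeted and leaves the averaging step unstated.
- **The interactions reveal nothing about switching.** With Table 1's score, the top adherence quintile gave 3.95, 3.71 and 3.28, closer to 4 than ITT. That is not the population average the SAP describes.

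If treatment in the interaction terms meant treatment received, the estimator would approach 4 under the SAP's assumptions, but the text specifies allocation. Had allocation been a predictor in the score model, which the SAP does not list, overlap was lost and the large-sample estimates were roughly 11 to 13.

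**Conclusion.** The point holds for the label and the interpretation. With baseline covariates and averaging, the propensity-quantile analysis estimates the effect of allocation, so it cannot serve as a check on switching. The all-treated sentences in sections 6 and 6.4 contradict Table 1.

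The gap between the two readings is 0.2 to 1.2 points of an assumed 4 if the arms' switching proportions sum to 5% to 30%. It is nil without switching. These figures rest on an assumed switching range and a constant effect.

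A reader might also infer that a complier estimate would justify the all-treated wording. It would not: it describes compliers, and extends to all participants only under further assumptions such as a constant effect. The correction should be made before the final analysis, but the primary model and its treatment-policy estimand need no change.

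**What to change.** 1. In SAP sections 6 and 6.4, describe the primary result and the propensity-quantile result as the effect of allocation regardless of switching. Delete both all-treated sentences. Stop calling the propensity-quantile analysis an adjustment for switching. If it is kept, restrict the score to baseline covariates, state that the estimate is averaged over quantiles, and align Table 1's description of the score with section 6.4. The balance check there refers to functional bracing, which is not an arm of this trial, and should be corrected too.
2. If an analysis that addresses switching is wanted, as section 6 says, define a separate supplementary estimand with an estimator that uses treatment received. One option is a complier-average causal effect at 12 months by two-stage least squares, with allocation as the instrument. State the exclusion restriction and monotonicity, and interpret the result as the effect in compliers. State how missing 12-month outcomes are handled, because a single-time-point model loses the repeated-measures handling.

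The first step costs only wording. The second adds one standard model, extra assumptions and a wider interval: at N = 266 the simulated sampling SD was 1.45, 1.54 and 1.77, against 1.28, 1.19 and 1.21 for ITT, so about 13% to 46% larger.

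### The propensity balance check in SAP 6.4 compares the wrong groups, by a different method from the one planned, so it cannot show whether the propensity model is adequate

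*SAP*

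**What the plan says.** All of this is in SAP section 6.4, Sensitivity Analysis.

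- **The score.** It comes from a logistic model, "modelling the probability of treatment received as a function of covariates that are prognostic for the outcome".
- **Its use.** In the regression adjustment, "we include the quantiles of the propensity score in the analysis model as covariates", with interactions between treatment and the quantiles. Table 1 describes the same approach.
- **The overlap plot.** "The distribution of the PS for each randomised group will be examined graphically".
- **The balance table.** Weighted balance is examined "between those who assigned to surgical fixation and those assigned to functional bracing". It "will be documented as standardised differences before and after weighting for each confounder used".
- **The trigger.** The sentence opens with a hedge, "Although, there is no definitive value at which the treatment is considered unbalanced", and then says that "a variance ratio less than 0.5 indicates that the data is not balanced". In that case the propensity model may need to be revisited, or observations with extreme weights trimmed or removed.

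Section 6.4 lists no covariates for the propensity model, does not say which group's variance is the numerator, sets no upper limit for the ratio and attaches no limit to the standardised differences.

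**The concern.** A balance diagnostic has one task: to show whether conditioning on the estimated score has made the groups that the score distinguishes comparable on the measured confounders. Here those groups are the children who did and did not have surgery. Section 6.4 departs from this in three ways.

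1. **Groups.** Balance and overlap are examined by assignment. Randomisation already balances the assigned groups in expectation, so a comparison between them before weighting says nothing about selective switching. Weights built for treatment received are not designed to balance the assigned groups and can unbalance them.
2. **Method.** The check and its remedy (trimming weights) belong to a weighted analysis. The analysis described uses quantiles and no weights.
3. **Trigger.** A variance ratio compares spread, not means, and a limit on one side only depends on which group is the numerator.

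Section 6 presents the adjustment for switching as a supplement to the intention-to-treat analysis. Section 4.2 turns to section 6.4 when deviations involve, for example, more than 5% of participants. If the diagnostic cannot tell a good propensity model from a poor one, readers have no basis for judging how far to trust that analysis.

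**Working it through.** The 0.5 cut-off is stated as a convention, so there is no derivation to reproduce. Two things can be checked: what the trigger responds to, and what a comparison by assignment shows.

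**1. The variance ratio for a binary covariate**

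With prevalences p1 and p0:

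- VR = p1(1-p1) / [p0(1-p0)]
- SMD = (p1-p0) / sqrt{[p1(1-p1) + p0(1-p0)] / 2}

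| p1 vs p0 | VR | absolute SMD | VR below 0.5? |
|---|---|---|---|
| 30% vs 70% | 0.21/0.21 = 1.00 | 0.40/sqrt(0.21) = 0.87 | no |
| 20% vs 50% | 0.16/0.25 = 0.64 | 0.30/sqrt(0.205) = 0.66 | no |
| 50% vs 10% | 0.25/0.09 = 2.78 | 0.40/sqrt(0.17) = 0.97 | no |
| 10% vs 50% | 0.09/0.25 = 0.36 | 0.97 | yes |
| 5% vs 50% | 0.0475/0.25 = 0.19 | 1.17 | yes |

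The third and fourth rows are the same imbalance with the groups exchanged. A limit of 2 on the other side would catch the third row but not the first. For a continuous covariate, a shift in mean of any size with equal spread gives VR = 1.

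**2. Assigned against received groups**

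The documents give no switching rates, so these inputs are assumptions: 1:1 allocation (from the documents) and one binary confounder X with prevalence 40%. In the non-operative arm, 20% of children with X and 5% without X have surgery. In the operative arm, 5% with X and 20% without X do not.

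- Switching overall: 0.5(0.4×0.20 + 0.6×0.05) + 0.5(0.4×0.05 + 0.6×0.20) = 12.5%.
- True score: with X, 0.5×0.20 + 0.5×0.95 = 0.575; without X, 0.5×0.05 + 0.5×0.80 = 0.425. Overall: 0.4×0.575 + 0.6×0.425 = 0.485.
- Received groups, unadjusted: prevalence of X is 0.230/0.485 = 0.474 with surgery and 0.170/0.515 = 0.330 without, so SMD = 0.30.
- Assigned groups, unadjusted: 40% in each, so SMD = 0.00.

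*Correct model.* Weights are 1/score for children who had surgery and 1/(1-score) for those who did not. The received groups are then balanced (SMD 0.00). Mean weights by assignment are:

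- operative arm: 0.95/0.575 + 0.05/0.425 = 1.77 with X; 0.80/0.425 + 0.20/0.575 = 2.23 without X;
- non-operative arm: 2.23 with X and 1.77 without X.

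Weighted prevalence of X is 0.4×1.77/(0.4×1.77 + 0.6×2.23) = 0.346 in the operative arm and 0.457 in the non-operative arm. SMD = -0.23 and VR = 0.91.

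*Model that omits X.* The score is 0.485 for everyone, so the weights are 1/0.485 = 2.06 for surgery and 1/0.515 = 1.94 for no surgery. Weighted prevalence by assignment is 0.402 in both arms, SMD 0.00. The received groups keep SMD 0.30.

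In this example the planned comparison looks clean for the model that fails and unbalanced for the model that is correct.

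**3. Simulation of the same set-up**

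There were 334 children and 1,000 runs in each of three scenarios. The set above was one. The other two changed the switching probabilities: 30% and 5% in the non-operative arm with 2% and 20% in the operative arm, and 50% and 5% with 5% and 20% (with X first each time). Overall switching was 12% to 18%.

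| Comparison, correct model | Mean SMD |
|---|---|
| Assigned, unweighted | 0.00 |
| Received, unweighted | 0.30 to 0.63 |
| Assigned, weighted | -0.23 to -0.37 |
| Received, weighted | 0.00 |

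A variance ratio below 0.5 did not occur in any run, for any of the four comparisons.

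**The case against.** **Standardised differences are planned.** The section documents them for every confounder, and they do respond to means, so an imbalance of 30% against 70% between the groups compared would be visible in the table. This stands, and the plan should be credited with it. It does not repair the check, because the differences are taken between assigned groups and nothing follows from their size.

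**The trigger is hedged.** The text says there is no definitive value and that the model may need revisiting. It never says that a ratio of 0.5 or more means balance. That is correct: 0.5 is a warning sign, not a pass mark. It is still the only numerical one.

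**The analysis is by allocation, so assigned groups are the natural comparison.** They are for the treatment effect. The adequacy of a score for treatment received can be judged only between the groups as treated.

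**The weighting text may be an extra check or a remnant.** This is plausible. Section 6.4 mentions several approaches but describes one, and a weighted analysis does exist in section 6.2, for the DASH sports module. That would be a reason to say where the weight-based check applies.

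**Stronger readings.** A reader might infer that the check would almost always report balance. The documents do not support that: weighting for treatment received can create apparent imbalance between assigned groups, as the working shows. Nor do they establish that the confounders are mainly binary. Section 6.4 names none; Table 6 is mostly categorical, but Table 7 holds scores summarised by means and SDs. The rule does flag some gross binary imbalance (5% against 50%), and the failure above 2 assumes a fixed numerator. The ratio can miss large imbalance; it does not always do so.

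**Conclusion.** Wrong as written, for a sensitivity analysis. The balance check does not match the propensity analysis it is meant to validate: it uses assigned rather than received groups and weights rather than quantiles, and it names a comparator that this trial does not have. These defects follow from the text alone.

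The figures are illustrations. Those in part 1 of the working are exact for the prevalences shown. Those in parts 2 and 3 rest on one binary confounder with 40% prevalence and 12% to 18% switching that depends on it. They show that the planned comparison can mislead in both directions; they do not predict what it will show in this trial. No effect on a treatment estimate has been quantified, and the primary intention-to-treat result does not depend on this check. It is worth correcting because the SAP relies on this analysis to deal with switching and the correction costs little.

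**What to change.** Revise the balance text in SAP section 6.4 as follows.

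1. Plot the score, and assess balance, between children who did and did not receive surgery.
2. Report standardised differences before and after adjustment for the propensity quantiles, pooled across quantiles.
3. Base the decision to revisit the model on the pooled differences, with a pre-specified limit that allows for chance variation at this sample size.
4. Use the variance ratio only for continuous covariates, and two-sided (outside 0.5 to 2).
5. Apply the weight-based check and trimming only where weights are used.
6. Replace functional bracing with non-operative treatment.

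Item 3 needs care. The standard error of a standardised difference under balance is about sqrt(1/n1 + 1/n0). In one fifth of 334 children (quintiles assumed), with about 33 per group at best, it is sqrt(2/33) = 0.25. A limit of 0.1 inside each quantile would then be exceeded by chance in about 70% of comparisons. Even with 167 per group it is sqrt(2/167) = 0.11, and a single covariate exceeds 0.1 by chance about 36% of the time. Hence the differences should be pooled and the limit set with these figures in view.

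The cost is SAP wording, slightly more diagnostic work and possibly more re-specification of the propensity model. No data collection changes.
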